3.5 EFFICACY MEASURES

3.5.1 Primary Efficacy Variable

The NCBRF-TIQ Conduct Problem subscale score is the primary efficacy variable.

The ratings from the NCBRF-TIQ scale are grouped into a single 10-item Positive Social subscale and the following 6 Problem Behavior Subscales: *Overly Sensitive* (4 items), *Oppositional Behavior* (9 items), *Conduct Problem* (14 items), *Hyperactivity* (4 items), *Inattention* (7 items), and *Withdrawal/Dysphoria* (16 items).

Each subscale score is the sum of the scores for the individual items included in the subscale. The Oppositional Behavior and Conduct Problem subscale totals can be combined into a DBD-Total score, and the Hyperactivity and Inattention subscales can be combined into an ADHD-Total score.

3.5.2 Secondary Efficacy Variables

CGI-S, CGI-I, ADHD-Inattention, ADHD-Hyperactivity/Impulsivity, and ADHD-Combined Subscale scores are the 5 secondary efficacy variables as described below.

The CGI scale was developed to provide a brief, stand-alone assessment of the clinician's view of a subject's global functioning prior to and after administration of a SM. Severity of illness (CGI-S) and global improvement (CGI-I) are both rated on a scale of 0 to 7 with 7 being "extremely ill" or "very much worse", respectively. Successful therapy is indicated by a lower overall score in subsequent testing.

- CGI-S will be evaluated by the Investigator at each visit on a 7-point scale with 1=Normal, 2=Borderline ill, 3=Mildly ill, 4=Moderately ill, 5=Markedly ill, 6=Severely ill, and 7=Extremely ill. CGI-S is a secondary efficacy variable.
- CGI-I, relative to the condition at baseline, will be evaluated by the Investigator at each post-baseline visit on a 7-point scale with 1=Very much improved, 2=Much improved, 3=Minimally improved, 4=No change, 5=Minimally worse, 6=Much worse, and 7=Very much worse. CGI-I is a secondary efficacy variable.

The SNAP-IV rating scale includes 18 ADHD and 8 oppositional defiant disorder (ODD) symptoms as specified in the DSM-IV-TR and International Statistical Classification of Diseases and Health Related Problems 10th Revision (ICD-10) Classification of Mental and Behavioral Disorders. The symptoms are scored by assigning a severity estimate for each symptom on a 4-point scale.

The ratings from the SNAP-IV scale are grouped into the following 3 subscales: ADHD-Inattention (items #1-9), ADHD-Hyperactivity/Impulsivity (items #10-18), and ODD (items #19-26). In addition, the first two subscales are combined to form the ADHD-Combined subscale. Each subscale score is the average of the scores for the individual items included in the subscale.

3.5.3 Exploratory Efficacy Variable

The ODD subscale score (items #19-26 from the SNAP-IV scale) is an exploratory efficacy variable.

NCBRF-TIQ subscale (*Overly Sensitive Oppositional, Hyperactivity, Inattention, and Withdrawal/Dysphoria*) scores are considered exploratory efficacy variables. Additional exploratory variables will be the DBD-Total score, and the ADHD-Total score from the NCBRF-TIQ.

3.6 SAFETY MEASURES

Safety measures during the study will consist of AE and SAE monitoring, clinical laboratory tests, vital signs, physical examinations, and 12-lead ECGs. Assessment of possible neurological side effects will be performed using the Simpson-Angus scale, Barnes Akathisia scale, and AIMS.

3.6.1 Adverse Events

For subjects who receive SM, all AEs (learned of through spontaneous reports or subject interview) will be collected starting from providing informed consent for study participation. Collection will continue through 7 days after the last dose of SM for non-serious AEs, and through the 30 day Follow-up Visit for SAEs. All AEs will be collected on the AE Case Report Form (CRF). SAEs will be reported if the Investigator believes the event is at least possibly related to SM. Investigator will assess the severity and the causality of AEs.

A cluster of signs and symptoms that results from a single cause should be reported as a single AE (e.g., fever, elevated WBC, cough, abnormal chest X-ray, etc. can all be reported as "pneumonia").

3.6.2 Clinical Laboratory Values

The Schedule of Visits and Procedures shows the time points at which blood and urine will be collected for clinical laboratory tests. Laboratory tests should be performed under fasting conditions. Any laboratory abnormality may qualify as an AE in the Investigator's judgment.

A complete list of all clinical laboratory assessments is presented in Table below.

Hematology	Serum Chemistry (fasting)	Urinalysis
Hematocrit Hemoglobin Red blood cell count (RBC) Platelet count White blood cell count (WBC) (with differential)	Albumin Alkaline phosphatase Alanine transaminase (ALT) Aspartate transaminase (AST) Bilirubin- Total and Direct Blood urea nitrogen (BUN) Calcium Chloride Cholesterol- Total, HDL and LDL Creatinine Creatine phosphokinase (CPK) Glucose Inorganic phosphorous Potassium Sodium Total protein Triglycerides Uric acid	Ketones Protein Specific gravity Glucose pH
Other tests		

Insulin Prolactin Urine drug panel for drugs of abuse (amphetamines, barbiturates, benzodiazepines, cocaine, marijuana/cannabinoids, methadone, opiates, phencyclidine, propoxyphene, and alcohol) Urine pregnancy test (for female subjects of menstruating age or ≥ 11 years old)
		

3.6.3 Vital Signs, Height, and Weight Measurements

Vital sign measurements (HR, blood pressure, temperature, respiratory rate) and height and weight will be obtained at all visits as designated on the Schedule of Visits and Procedures. Blood pressure and pulse will be measured after the subject has been sitting for 5 minutes. Pulse should not be recorded on Screening and Final Visits when ECGs are performed.

3.6.4 Medical History and Physical Examinations

Medical history will be taken at the screening visit. Physical examinations will be performed at the Screening visit and Final Visit as designated on the Schedule of Visits and Procedures.

3.6.5 Electrocardiograms (ECGs)

ECGs (12-lead) will be obtained at the Screening visit and the Final Visit as designated on the Schedule of Visits and Procedures. Additional ECGs may be performed at other times if deemed necessary.

The ECG will be recorded while the subject is resting in a supine position. The ECG will electronically measure the PR, QRS, QT, and QTc intervals, and heart rate.

All ECG tracings will be reviewed within 24 hours by the Investigator or sub-Investigator. PR intervals will be determined for each of these ECGs from a single reading. Invalid

measurements will be repeated. QTc will be reported as QTcF (QT corrected using Fridericia's method).

3.6.6 Concomitant Medications

For subjects who receive SM, concomitant medications and therapies that are ongoing as of the date of informed consent will be recorded on the Concomitant Medication CRFs. The Investigator will record all concomitant medications, including over-the-counter medications, on the Concomitant Medication CRF. The Investigator will record the AE for which the concomitant medication was administered on the AE CRF.

3.6.7 Other Special Tests for Extrapyramidal Symptoms (EPS)

Simpson-Angus Scale

The Simpson-Angus scale is a 10-item rating scale that is widely used for assessment of neuroleptic-induced Parkinsonism. It consists of 1 item measuring gait, 6 items measuring rigidity, and three items measuring glabella tap, tremor and salivation, respectively. This assessment will be administered at all post-screening study visits.

Barnes Akathisia Scale

The Barnes Akathisia scale is a rating scale for drug-induced akathisia and includes components for rating the observable, restless movements characteristic of akathisia, the awareness of restlessness, and any distress associated with the condition. This assessment will be administered at all post-screening study visits.

Abnormal Involuntary Movement Scale (AIMS)

The AIMS test is a rating scale used to measure tardive dyskinesia. There are 12 items that rate involuntary movements of various areas of the subject's body. This assessment will be administered at all post-screening study visits.

3.7 COMPLETION/DISCONTINUATION OF SUBJECTS

Subjects will be permitted to leave the study at any time. Subjects can be withdrawn from the study in any of the following circumstances:

- SAE or an AE
- Administrative reasons (e.g., sponsor decision)
- Withdrawal of consent/assent
- If the subject becomes pregnant
- If it is in the best interest of the subject, in the opinion of the Investigator
- Termination of the study.

When an event such as a family emergency, a transient illness (such as a cold) unrelated to SM, or a remediable act of non-compliance prevents a subject from participating in a scheduled visit, but the subject wishes to continue in the study, the Investigator will attempt

to reschedule the visit and retain the subject in the study on a case by case basis, rather than discontinue the subject's participation.

If a subject is prematurely discontinued from participation in the study for any reason after SM administration, the Investigator must make every effort to perform the Final Visit assessments.

4. DATA ANALYSIS

Tabular summaries of the data collected during the study will be presented to provide a general description of the subjects studied and an overview of the efficacy and safety results. Data from all sites will be combined in the computation of these summaries, and summaries will be presented by treatment group. Within each treatment group, summaries will also be presented by weight category at baseline ($< 30\text{kg}$, $\geq 30\text{kg}$), where appropriate. All subjects randomized to Treatment 4, whether they are maintained on Treatment 4 or reduced to Treatment 3, will be analyzed under the Treatment 4 group. Continuous variables will be summarized using descriptive statistics (number of subjects, mean, standard deviation [SD], median, and minimum and maximum values). Categorical (nominal) variables will be summarized using frequency tables (number and percentage of subjects in each category). If some values are missing, the percentages will sum to less than 100%.

In addition to tabular summaries, subject data listings will be provided. All data collected on CRF and from central laboratory will be presented in data listings. Where appropriate, data will be summarized for each protocol-specified visit. Unscheduled data will be listed but not summarized.

4.1 ANALYSIS POPULATIONS

The enrolled population consists of all subjects with ICFs signed by their parent or LAR (and IAFs signed by the subjects, where applicable).

The safety population consists of all randomized subjects who receive at least 1 dose of SM.

The intent-to-treat (ITT) population consists of all safety population subjects with at least 1 post-baseline efficacy assessment.

The restricted ITT population consists of all ITT population subjects with at least 1 efficacy assessment during the Maintenance Period.

The PK population consists of safety population subjects with at least 1 PK measurement.

The safety, ITT, restricted ITT, and PK populations are based on actual treatment received. Table 4.1.1 provides these analysis populations for all randomized subjects.

Listing 4.1.1 provides inclusion and exclusion criteria violations for all randomized subjects. Listing 4.1.2 gives analysis populations.

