3.3 RANDOMIZATION PROCEDURE

The randomization for this study will be managed centrally by an IVRS vendor; specific instructions to conduct subject randomization will be provided in a separate document to all investigational sites, along with site staff access to the system.

A randomization scheme will be generated using a pseudo-random number generator in a computer program. The method avoids bias by use of a chance mechanism. Within each weight group, the randomization scheme assigns Treatment 1, Treatment 2, Treatment 3, or Treatment 4 to each randomization number in a 1:1:1:1 ratio.

Upon admission to the study, subjects will be assigned a 4-digit screening number, in the order that they are entered. Subjects who subsequently meet all eligibility criteria will be assigned a 6-digit randomization number. The first 3 digits will refer to the site, and the last 3 will refer to the subject-specific number, which will be assigned according to the randomization scheme.

Once a randomization number has been assigned, no attempt should be made to use that number again, if, for example, a subject is withdrawn. All subjects are randomized only once.

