3.4 SCHEDULE OF VISITS AND PROCEDURE

All subjects who are randomized and take any SM will be followed according to the protocol, unless consent for follow-up is withdrawn. The Sponsor, or the Sponsor's designee, must be notified of all deviations from the protocol visits or procedures and these procedures, if applicable, will be rescheduled or performed at the nearest possible time to the original schedule.

The exhibit on the next page presents the schedule of visits and procedures for the study.

Exhibit: Schedule of Visits and Procedures

PERIOD	Screening	Titration					Maintenance					Final Visit ^k	Follow-up	
		1	2	3 ^b	4 ^c	5 ^d	6	7	8	9	10	11		
VISIT	0													
WEEK	0	1	2	3 ^b	4 ^c	5 ^d	1	2	3	4	5	6	7	
WINDOW (DAYS)	Within 28 days prior to dosing	± 1	± 1	± 1	± 1	± 1	± 2	± 2	± 2	± 2	± 2	± 2	± 3	
Informed Consent/Assent ^a	X													
IVRS Call	X	X											X	
K-SADS-PL	X													
IQ Test (KBIT-2) ^e	X													
Inclusion/Exclusion Criteria	X	X												
Randomization		X												
Medical History	X													
Demographics	X													
Physical Examination	X												X	
ECG (12-lead)	X												X	
Vital Signs, height, and weight ^f	X	X	X	X	X	X	X	X	X	X	X	X	X	
Hematology/chemistry	X							X					X	
Urinalysis	X							X					X	
PK Blood Sampling			X	X					X ⁱ				X ⁱ	
Urine Drug Screen	X												X	
Urine Pregnancy Test ^g	X												X	
Efficacy Scales (NCBRF-TIQ, CGI, SNAP-IV)	X ^h	X	X	X	X	X	X	X	X	X	X	X	X	
Safety Scales (Simpson-Angus, Barnes, AIMS)		X	X	X	X	X	X	X	X	X	X	X	X	
Adverse Events	X ^j	X	X	X	X	X	X	X	X	X	X	X	X	X ^l
Concomitant Medications	X	X	X	X	X	X	X	X	X	X	X	X	X	
Drug Return and Compliance			X	X	X	X	X	X	X	X	X	X	X	
Drug Dispensation			X	X	X	X	X	X	X	X	X	X	X	

CONFIDENTIAL MATERIAL

This material is the property of Supernus[®] Pharmaceuticals, Inc.
and must not be disclosed or used except as authorized in writing by Supernus[®] Pharmaceuticals, Inc.

- a Written consent must be obtained prior to performing any study-related procedure.
- b For subjects receiving Treatments 2, 3 and 4 only.
- c For subjects receiving Treatment 3 and 4 only.
- d For subjects receiving Treatment 4 only.
- e IQ test to be administered if not performed 12 months prior to screening.
- f Heart rate (HR), blood pressure, temperature, respiratory rate, and weight will be measured weekly. Height will only be measured at Screening and Final Visit.
- g To be performed for female subjects of menstruating age or \geq 11 years old.

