4.5 POTENTIAL EXCLUSIONS FROM ITT POPULATION

Study data will be examined during the Data Review (described below in section 4.6) for potential exclusions from ITT population. ICH E9 guideline outlines circumstances where it will usually be acceptable to omit subjects from the ITT population without causing bias. Some of the potential exclusions in this study are:

- Subjects who violate the inclusion/exclusion criteria;
- Subjects who fail to take at least one dose of study medication;

- Subjects who do not provide any post-baseline data;
- Enrollment of a subject who did not meet all inclusion/exclusion criteria which would affect subject safety or would negatively impact data integrity;
- Use of any prohibited concomitant medication that may confound study results;
- Subject dosing error that results in a serious adverse event;
- Having any non-compliance issues raised by the investigator or sponsor prior to breaking the blind;
- Study visit or procedure conducted outside of required time frame that may negatively affect subject safety;
- Subject visit/procedure falls outside of the window of time indicated by the protocol resulting in increased potential for risk to the subject or any damage to the integrity or completeness of the data.

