5.1.2 Treatment Comparisons

Statistical testing to compare treatment groups (overall and pairwise) will be performed for the ITT population only using appropriate statistical methods, as described in the efficacy subsections below. Dose-response relationship will be assessed based on a review of the results of the complete set of pairwise comparisons of Treatment 1 vs. Treatment 2, Treatment 2 vs. Treatment 3, and Treatment 3 vs. Treatment 4, without adjustment for

multiple testing. Given the small per-treatment group sample size for the study, the resulting p-values from the statistical testing will be used for descriptive purposes only (i.e., not for inferential purposes), primarily as an aid in the clinical interpretation of the efficacy results.

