5.2.2 Results of Primary Efficacy Analysis

The changes from baseline in the NCBRF-TIQ conduct problem subscale scores at each post-baseline visit and endpoint will be compared among treatment groups using Kruskal-Wallis test (for the overall comparisons) and Wilcoxon rank-sum test (for the pairwise comparisons of Treatment 1 vs. Treatment 2, Treatment 2 vs. Treatment 3, and Treatment 3 vs. Treatment 4) for the ITT population. The Hodges-Lehmann estimators and associated 95% confidence intervals will be calculated for the median differences between Treatment 1 and Treatment 2, Treatment 2 and Treatment 3, and Treatment 3 and Treatment 4 (Hollander M, 1999). Table 5.2.2.1 provides the primary efficacy results for overall and pairwise comparisons for NCBRF-TIQ conduct problem subscale for the ITT population. Table 5.2.2.2 provides the summary statistics for NCBEF-TIQ conduct problem subscale for the restricted ITT population.

Listing 5.2.2.1 provides NCBRF-TIQ conduct problem subscale data for the ITT population.

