5.5 SENSITIVITY ANALYSIS

As a sensitivity analysis, the changes from baseline in the NCBRF-TIQ conduct problem subscale scores at each post-baseline visit and endpoint will be compared among treatment groups using analysis of covariance (ANCOVA) with treatment and weight group as the main factors and the baseline value as the covariate. Table 5.5.1 provides the sensitivity analysis results for NCBRF-TIQ conduct problem subscale for the ITT population.

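### SAP Section 4.1 groups the ITT and restricted ITT populations by treatment received, although ITT carries all the between-group efficacy tests (minor)

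*SAP*

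**What the plan says.** SAP Section 4.1 first defines who belongs to each population. Safety needs randomisation and a dose, ITT adds a post-baseline efficacy assessment, restricted ITT adds one in the Maintenance Period, and PK needs a PK measurement. It then states: "The safety, ITT, restricted ITT, and PK populations are based on actual treatment received".

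The efficacy sections rest on ITT:

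- Section 5.1.2: "Statistical testing to compare treatment groups (overall and pairwise) will be performed for the ITT population only".
- Section 5.2.2 (Kruskal-Wallis, Wilcoxon and Hodges-Lehmann): "Table 5.2.2.1 provides the primary efficacy results for overall and pairwise comparisons for NCBRF-TIQ conduct problem subscale for the ITT population".
- Section 5.5 (ANCOVA): "Table 5.5.1 provides the sensitivity analysis results for NCBRF-TIQ conduct problem subscale for the ITT population".
- Sections 5.3 and 5.4 run the secondary and exploratory tests on ITT too. Restricted ITT receives summary statistics only.

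Three other places bear on grouping. Section 4 says that all subjects randomised to Treatment 4, "whether they are maintained on Treatment 4 or reduced to Treatment 3, will be analyzed under the Treatment 4 group". Section 4.2 tabulates reasons for discontinuation by randomised group. The opening of Section 6 summarises safety by the treatment actually received.

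**The concern.** An intention-to-treat comparison keeps each subject in the group to which chance assigned him or her. Section 4.1 gives the population that name but forms its groups by what was taken. The tests, the Hodges-Lehmann estimates with their confidence intervals, and the dose-response review built on the pairwise comparisons would all use as-treated groups under an ITT label. For any subject given another arm's regimen, the comparison is no longer protected by randomisation. A reader of the tables would also assume randomised grouping from the label.

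**Working it through.** **Is the sentence about grouping or only about membership?** The sentences before it already settle membership in full, so it would add nothing as a membership rule. Section 6 uses nearly the same phrase, and there it plainly says how subjects are grouped. Section 4.2 names the randomised group instead, so the plan distinguishes the two bases. The sentence is a grouping rule.

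**Does another section restore randomised grouping for ITT?** Section 4 does so for one case, the reduction from Treatment 4 to Treatment 3. Sections 5.1 to 5.5 contain no such statement. Nothing covers a subject in any arm who is given a different arm's regimen.

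**Whom does the rule move?** Footnotes b to d of the visit schedule in Section 3.4 use treatment labels for subjects who are still titrating; footnote b reads "For subjects receiving Treatments 2, 3 and 4 only". On that usage, treatment received means the regimen being followed. It equals the randomised group unless a subject was put on another arm's regimen.

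**How much can one such subject matter?**

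Inputs: 72 randomised and 60 expected to complete (Section 3.2); 1:1:1:1 allocation within weight group (Section 3.3).

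- The plan's own figure: 72 × (1 − 0.17) = 59.76, about 60. It reproduces and does not depend on this point.
- Per arm: 72/4 = 18 randomised; 60/4 = 15 completers.

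Assumptions: 18 per arm in ITT, two adjacent arms (N = 36), no ties, and one subject of rank r counted in arm B instead of arm A.

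- Before: SD(U) = √(18 × 18 × 37/12) = 31.61 and E(U) = 18 × 18/2 = 162.
- After (17 v 19): SD(U) = √(17 × 19 × 37/12) = 31.56 and E(U) = 17 × 19/2 = 161.5.
- U = rank sum − n(n+1)/2. The rank sum of A falls by r, and n(n+1)/2 falls from 171 to 153, that is by 18. So U changes by 18 − r, and U − E(U) changes by 18.5 − r.
- Extreme rank (r = 36 or 1): 17.5/31.56 = 0.55 in z.
- Middle rank (r = 18 or 19): 0.5/31.56 = 0.02 in z, effectively nothing.
- With 15 per arm, the extreme is 14.5/√(14 × 16 × 31/12) = 14.5/24.06 = 0.60.

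One subject is 1/18 = 5.6% of an arm. The extreme value is a ceiling: it needs a wrong-regimen subject who also has the best or worst change score of the pair of arms. A sum of 14 item scores may well produce ties, so the no-ties figure is approximate.

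**The case against.** The strongest reply is that the sentence may never move anyone. If treatment received means the regimen followed, it coincides with the randomised group for every correctly supplied subject. Allocation is central ("The randomization for this study will be managed centrally by an IVRS vendor"), and the one dose change permitted by design is already handled as randomised. P-values are for description only, efficacy is a secondary objective, and the sample size has no statistical basis. Section 4.6 also schedules a review of the population definitions before database lock. All of this stands and limits the consequence. It does not make the rule right, and a scheduled review does not itself correct the sentence.

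Three stronger readings are tempting, and the document supports none of them:

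- *Dose-reduced Treatment 4 subjects would be counted in Treatment 3, so poor responders or poor tolerators would be shifted selectively.* Section 4 rules this out expressly.
- *A subject who stops during titration would be counted in a lower arm, having reached only that arm's dose level.* The wording does not exclude this in so many words, but the Section 3.4 footnotes label titrating subjects by assigned regimen, which is the more natural reading.
- *The plan itself foresees subjects changing arm, because Section 4.5 lists "Subject dosing error that results in a serious adverse event".* A missed, doubled or mistimed dose also fits that item, which is a possible ground for exclusion and not for regrouping. It does not show that wrong-arm dosing is expected.

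**Conclusion.** The point holds as a minor one. Section 4.1 states a grouping rule for ITT and restricted ITT that is not intention-to-treat, and it governs every between-group efficacy comparison. Its effect is confined to subjects given another arm's regimen. It is zero if there are none, and the SAP gives no rate from which to expect any. For one such subject, the pairwise Wilcoxon z moves by between about 0 and 0.55 (18 per arm, no ties; up to 0.60 with 15 per arm). Because the tests are descriptive, no decision rule turns on that shift. The conclusion rests on reading treatment received as the regimen followed. For safety and PK, grouping by treatment received is ordinary and is not in question.

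**What to change.** Replace the sentence in Section 4.1 with:

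> The ITT and restricted ITT populations are analysed by randomised treatment group; the safety and PK populations are analysed by actual treatment received, with Treatment 4 subjects reduced to Treatment 3 kept in Treatment 4 as stated in Section 4.

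The basis for safety and PK stays as it is, and Section 6 needs no change. The cost is one sentence of SAP wording, with no new data, tables or analyses. It is best made before database lock, and the data review in Section 4.6 is a convenient occasion.
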